## 4. F. Measurement of Treatment Failure During Initial Hospitalization.

We have modified the definition of Niewoehner {{387 Niewoehner, D.E. 1999}}as follows: treatment failure during the initial hospitalization will include all-cause death, need for intubation and mechanical ventilation, post-randomization use of noninvasive ventilation, or intensification of pharmacologic treatment. Intensification of pharmacologic treatment

will be defined as an increased dose of systemic steroids (higher dose or longer duration), increased use of antibiotics (change in antibiotic or longer course), addition of theophylline, increased liter flow of supplemental oxygen > 2 at rest, and increase in frequency or dose of inhaled bronchodilators.

**4. G. Quality of Life and Functional Status.** Patients will complete a general and disease-specific self-administered quality of life and functional questionnaires. We will use EQ-5D and the St. George's Respiratory Questionnaire (SGRQ). Both are validated tools extensively used in COPD.{{1167 Meguro,M. 2007}}{{1166 Pickard,A.S. 2008}}

**4. H.** Columbia–Suicide Severity Rating Scale (C-SSRS). The Columbia–Suicide Severity Rating Scale (C-SSRS) is a 2-page questionnaire that

prospectively assesses suicidal ideation and behavior using a structured interview face to face for patient responses. The C-SSRS will be performed during each evaluation visit according to the assessment schedule on Figure 4. Suicidal ideation is classified on a 5-item scale: 1 (wish to be dead), 2 (nonspecific active suicidal thoughts), 3 (active suicidal ideation with any methods [not plan] without intent to act), 4 (active suicidal ideation with some intent to act, without specific plan), and 5 (active suicidal ideation with specific plan and intent). The C-SSRS also captures information about the intensity of ideation, specifically the frequency, duration, controllability, deterrents, and reasons for the most severe types of ideation. Suicidal behavior is classified on a 5-item scale: 0 (no suicidal behavior), 1 (preparatory acts or behavior), 2 (aborted attempt), 3 (interrupted attempt), and 4 (actual attempt). The C-SSRS will be performed during each evaluation visit according to the assessment schedule (see Figure 4). During visit, patients will complete the assessment with the health professional. Patients who do not have suicidal behavior or ideation will answer a limited number of questions and will usually complete the assessment in approximately 3 minutes. Patients with significant suicidal ideation and/or behavior may require up to 10 minutes to answer all relevant questions.

The patient should not be released from the evaluation site until it is confirmed

that the patient is not considered to be at any suicidal risk and all responses negative to the C-SSRS.

Positive reports are generated for any of the following findings:

- Suicidal ideation with intention to act (score of "4")
- Suicidal ideation with specific plan and intent (score of "5")
- Made suicide attempt
- Interrupted suicide attempt
- Aborted suicide attempt
- Preparatory behaviors for making a suicide attempt

At Screening (Visit 1), the C-SSRS will be completed for the patient's lifetime history

of suicidal ideation and behavior. At all other visits, the C-SSRS will be completed for Version 04.13.2015

ideation and behavior since the previous visit. The patient's responses should remain negative throughout the entire trial. If a possible exclusion alert is triggered

by a positive response at Screening (Visit 1), 2 additional questions at the bottom of the

report will need to be asked to determine whether exclusion criteria 9a and/or 9b have

been met. A response of "Yes" to either one or both of the follow-up questions will exclude the patient from the trial and necessitate immediate psychiatric referral of the patient on the same date as the screening visit. For all subsequent visits after Screening (Visit 1), if the patient's response generates a change in the findings report from negative to positive, the patient should be referred for immediate psychiatric evaluation on the same date as the site visit and the PI will should be contacted. Positive suicidality indication findings reports after the Screening Visit (Visit 1), if confirmed by the *Investigator*, should be considered to be an AE. SAEs must be *reported* as outlined in Section 6. Ultimately, the determination of suicidality and risk is up to the *Investigator*'s clinical judgment.

**4. I. Measurements of Dyspnea.** Dyspnea will be measured by use of the modified Medical Research Council Dyspnea score. This is a well-known, validated and easy to use scale that is a reliable and sensitive tool specific to COPD patients that will allow detection of a response to therapy as well as comparison to other studies reporting dyspnea as an outcome in other COPD trials.

**4.** J. Description of Optimized Standard Care for COPD Exacerbations. All patients will receive standardized, optimized care for AECOPD {{387 Niewoehner,D.E. 1999}}. Nebulized albuterol (2.5 mg in 0.5 ml, dilute to 3 ml NSS administered every 4-6 hours) and ipratropium bromide (0.5 mg in 0.5 ml, diluted with 2.5 ml of saline administered every 6 hours) will be given. A 14-day course of systemic steroids consisting of intravenous methylprednisolone 125 mg every 6 hours for up to 72 hours, followed by once daily oral prednisone 60mg/day for days 4-7, 40 mg prednisone days 8-11 and 20 mg prednisone days 12-14 will be provided. A 7-day course of antibiotics will be selected based on patient's medical allergy history and relevant culture data if available. Supplemental oxygen will be provided by route and dose to achieve maximum patient comfort and compliance to maintain a  $SaO_2 > 92\%$ . Noninvasive positive pressure ventilation will be utilized at the discretion of the treating physicians but will follow accepted guidelines {{133 Keenan,S.P. 2003; 136 Lightowler,J.V. 2003}}.

**4. K. Intervention with Roflumilast.** An IND for using roflumilast will not be required because this is an FDA approved medication for oral use and we are not seeking a change in label indications.

**4. L. Drug/Placebo supply.** Roflumilast and matching placebo will be provided by Forest Laboratories and stored by the Investigational Pharmacy Unit at Temple University Hospital.

**4. M. Pharmacokinetics of Roflumilast.** Following oral administration, roflumilast is rapidly absorbed with a  $t_{max}$  of about 1 hour and an 80% bioavailability. Roflumilast shows linear dose-proportional pharmacokinetics over a dose range of 250-1000 ug and plasma disposition half-life is about 10-20 hours making once daily dosing a feasible option. roflumilast is metabolized by CYP3A4 and CYP1A2 enzymes with N-oxide being the principal major metabolite. N-oxide has selectivity for the PDE4 isoenzyme and

mainly accounts for roflumilast's in vivo bioactivity. No major interactions have been reported between roflumilast and other COPD medications.

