## 4. Methods:

**4. A. Study Population.** 100 AECOPD patients hospitalized at Temple University Hospital, Temple University Episcopal Hospital Campus, Jeanes Hospital and St Mary's Hospital.

**Inclusion Criteria.** Primary diagnosis of AECOPD defined as acute increase in dyspnea, sputum volume, and/or sputum purulence without other identified cause; consent obtained and treatment started before discharge from the hospital ; patient age >40, < 80 years old; cigarette smoking  $\geq$  10 pack-years; informed written consent.

**Exclusion Criteria.** Prior diagnosis or high suspicion for asthma based on investigator judgment; pulmonary edema, pneumonia, interstitial lung disease or significant Version 04.13.2015

bronchiectasis based on admission chest x-ray; intubated and mechanically ventilated at the time of evaluation; active liver disease, or transaminase elevations ( $\geq$  3xULN); history of alcoholism or heavy ethanol use; history of suicidal behavior  $\leq$  2 years or suicidal ideation  $\leq$  6 months prior to enrollment; pregnant or lactating females. Those on the following excluded medications: P450 inducers (e.g., rifampicin, phenobarbital, carbamazepine, and phenytoin) and CYP3A4 inhibitors or dual inhibitors that inhibit both CYP3A4 and CYP1A2 simultaneously (e.g., erythromycin, ketoconazole, fluvoxamine, enoxacin, cimetidine.

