## 4. Q. Assessment of effectiveness.

The present proposal is a pilot study designed to test the feasibility of a future project to be conducted in a multicenter trial in hospitalized patients, to determine the tolerance of roflumilast in hospitalized COPD patients, and to determine the treatment effect of roflumilast to decrease all-cause mortality and all cause readmission rate as add-on therapy. The specifics aims will be:

- 1. Determine the tolerance of roflumilast in hospitalized COPD patients
- 2. Determine the treatment effect of roflumilast as add-on therapy to decrease all cause readmission and mortality as a composite endpoint 180 days after randomization to roflumilast or matching placebo ≤ 12 hours after hospitalization for acute COPD exacerbation.

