## 4. R. Statistical analysis plan.

The primary analysis for all study outcomes will be performed on an intention to treat basis. In the intention to treat approach, all subjects are analyzed in the group to which they were randomized, regardless of whether the assigned treatment was adhered to and regardless of whether there were any eligibility violations.

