## 4. Assessment of treatment effect

In this pilot proposal, the treatment effect of roflumilast vs. placebo to prolong the time to event of a combined endpoint of death or re-hospitalization will be assessed in an intention to treat manner. In a similar manner, the treatment effect of roflumilast vs. placebo to effect all of the secondary endpoints proposed to be measured in the pivotal phase III trial will also be measured (time to respiratory death or respiratory re-hospitalization during the 180 days post-randomization; rate of death or readmission at 30 days post-discharge; treatment failure [see definition below]; change in health status, change in FEV1, and dyspnea during the 180 days post-randomization; length of hospital stay during the index hospitalization; and the tolerance of roflumilast vs. placebo in hospitalized AECOPD).

Because this is a pilot study the intent is to see if there is a signal that would justify a larger clinical trial. Therefore the significance level has been set to 0.1 and the power has been set at 0.7. A total of 100 patients will enter this two treatment parallel-design study. The probability is 70 percent that the study will detect a treatment difference at a two sided 10.0 percent significance level, if the true hazard ratio is 1.654. This is based on the assumption that the accrual period will be 36 months and the follow up period will be 6 months and the median time to event is 8 months. The total number of events will be 73.

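### The treatment-failure definition counts noninvasive ventilation that merely continues from before randomization, so a patient still on it is a failure in either arm

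*Combined protocol and SAP*

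**What the plan says.** - **Eligibility (4.A).** The only ventilation exclusion is for patients "intubated and mechanically ventilated at the time of evaluation". Neither the inclusion nor the exclusion criteria mention NIV.
- **Background care (4.J).** "Noninvasive positive pressure ventilation will be utilized at the discretion of the treating physicians", following accepted guidelines.
- **Endpoint (4.F).** Failure during the index stay is death from any cause, intubation with mechanical ventilation, "post-randomization use of noninvasive ventilation, or intensification of pharmacologic treatment". Intensification "will be defined as an increased dose of systemic steroids (higher dose or longer duration", and the rest of that list (antibiotics, theophylline, oxygen flow, bronchodilators) is likewise worded as an increase, a change or an addition.
- **Role (4.R, Assessment of treatment effect).** In the pilot, the effect on "all of the secondary endpoints proposed to be measured in the pivotal phase III trial will also be measured"; treatment failure is on the list that follows.
- **Analysis set (4.R).** "The primary analysis for all study outcomes will be performed on an intention to treat basis", so patients on NIV at randomization stay in the comparison.
- **Timing.** Section 4.Q places randomization no more than 12 "hours after hospitalization for acute COPD exacerbation". Section 4.A asks only for "consent obtained and treatment started before discharge from the hospital". The outcomes text under 3.B contains both statements.

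**The concern.** Within one definition, the drug component is worded as a change in treatment and the NIV component as use. Limiting it to the period after randomization removes NIV that had already ended. It does not remove NIV that runs across randomization, because the next session is use after randomization.

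Patients in that position carry no information on the treatment effect on this endpoint. They raise the failure rate in both arms and pull the difference toward zero, so the endpoint partly records severity at entry. Section 3.A says that the pilot is meant to supply the treatment effect for powering a phase III trial. An inflated failure rate and an attenuated effect would carry into that planning. Sites could also classify the same patient differently, depending on whether they read the component as any use or as new use.

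**Working it through.** **1. The plan's own figure.** No rate, effect or power is stated for treatment failure. The only power statement concerns the primary endpoint: hazard ratio 1.654, two-sided 0.10, 70% power, 73 events. The Schoenfeld formula gives 4 × (1.645 + 0.524)² / (ln 1.654)² = 74.3 events, and 73 events give 69.3% power. The event count and power agree with each other but say nothing about treatment failure.

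**2. Classification as written.**

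| NIV course | Failure through the NIV component? |
|---|---|
| Ended before randomization, not used again | No |
| Running at randomization and continued, including the next intermittent session | Yes, in either arm |
| First started after randomization | Yes |

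The second row is the problem.

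**3. Dilution formula.** Let f be the share, equal in expectation across arms, whose NIV carries over, and p the failure risk among the others. Then:

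- observed risk = f + (1 − f)p
- observed difference = (1 − f)(p_placebo − p_roflumilast)

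For any f above zero, a true difference among the others is shrunk.

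**4. Illustration.** From the documents: 100 patients and two-sided 0.10. Assumed: 1:1 allocation (the ratio is not stated), p = 30% vs 15%, the values of f, and a comparison of two proportions (4.R names no method for this endpoint). The f = 0 row represents the corrected definition only if patients on NIV at entry then have the same risks as the others.

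Worked case, f = 10%:
- Risks: 0.10 + 0.90 × 0.30 = 0.370 and 0.10 + 0.90 × 0.15 = 0.235; difference 0.135.
- Standard error: √[(0.370 × 0.630 + 0.235 × 0.765)/50] = 0.0909, so z = 1.49.
- Power: Φ(1.49 − 1.645) plus the negligible opposite tail, about 44%.

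| f | Observed risks | Difference (points) | Power |
|---|---|---|---|
| 0% | 30.0% vs 15.0% | 15.0 | 57% |
| 2% | 31.4% vs 16.7% | 14.7 | 54% |
| 5% | 33.5% vs 19.25% | 14.25 | 50% |
| 10% | 37.0% vs 23.5% | 13.5 | 44% |
| 20% | 44.0% vs 32.0% | 12.0 | 35% |
| 30% | 51.0% vs 40.5% | 10.5 | 28% |

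Using the pooled variance under the null gives 56%, 43%, 34% and 28% at f = 0, 10, 20 and 30%. With an assumed 40% vs 20% (pooled), power is 71% at f = 0, 59% at 10% and 49% at 20%.

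**5. A less favorable case for the fix.** Suppose f = 10% and, under the corrected definition, these patients fail at 50% in both arms through the other components. The risks are 0.10 × 0.50 + 0.90 × 0.30 = 0.320 and 0.10 × 0.50 + 0.90 × 0.15 = 0.185. The difference is still 13.5 points. Power is about 47%, against 44% as written.

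**The case against.** **The authors probably meant new use.** Among the components, only NIV carries the restriction to the period after randomization, which suggests that earlier NIV was to be left out. This reading of the intent is fair. The text still does not settle NIV in progress at randomization, and applied literally it counts it.

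**The share may be small.** Section 4.A requires written consent. Questionnaires and spirometry come before randomization in the outcomes text (4.D lets spirometry wait until the patient is able), and a face-to-face suicidality interview is part of screening. Entry near discharge would lower the share further. This stands as a reason to expect less than 20–30%: at 2–5% the illustrated loss is about 3 to 7 points of power. It does not make the share zero, because a patient between NIV sessions can complete these steps, and the 12-hour wording would raise the share. The two timing statements need to be reconciled in any case.

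**The consequence is limited.** This is one secondary endpoint in a pilot, with no stated target. By randomization, the certain failures fall in both arms in expectation and favor neither. That stands.

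Two stronger readings are tempting, and the documents support neither:
- A reader might infer that everyone on NIV at entry fails at time zero. They fail only if NIV continues or resumes after randomization during the index stay, and 4.F sets no time scale for the endpoint.
- A reader might extend the point to the ventilation aim in 3.A. That aim is worded as need for ventilation and belongs to the phase III aims. Neither the outcomes list under 3.B nor the pilot's list in 4.R contains a separate ventilation outcome.

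**Conclusion.** The point holds for treatment failure as worded in 4.F. The rule misclassifies patients whose NIV continues across randomization: they count as failures regardless of assignment, which raises the failure rate and multiplies the risk difference by (1 − f). The direction is certain whenever f is above zero and a true effect exists among the other patients.

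The size cannot be determined from the documents. The illustrated fall from 57% power to 50%, 44% or 35% at f of 5%, 10% or 20% rests on assumed failure rates, 1:1 allocation, and equal risks after the fix for patients on NIV at entry. If those patients respond less, correcting the wording recovers less. The primary endpoint, time to death or re-hospitalization, is untouched. This is a modest defect with a cheap remedy, and worth correcting because the pilot's estimates are meant to inform a larger trial.

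**What to change.** In 4.F, define the NIV component as a change from status at randomization, in line with the pharmacologic component:

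- **Not on NIV at randomization:** new initiation of NIV after randomization.
- **On NIV at randomization:** a pre-specified escalation of NIV, or its resumption after a pre-specified NIV-free interval.

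Continued or intermittent sessions of the same course then do not count. The interval is essential: if any restart counted, the next session of intermittent NIV would again be a failure. Without the escalation clause, worsening in patients who stay on NIV would be missed. The investigators need to set both thresholds in advance, as outcome definitions only.

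Record NIV status at randomization and report treatment failure by that status. Whether it is already collected cannot be judged, since the case report form is not in the documents and Figure 4 is not shown.

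The cost is a short redraft of 4.F, at most one added data item and one descriptive breakdown. Eligibility and care are unchanged, and 3.A needs no edit for the pilot. The downside is small: for patients on NIV at entry, failure rests mainly on death, intubation and pharmacologic intensification.

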## 4. N. Contraindications and side effects to the use of Roflumilast.

**1. Contraindications**: Roflumilast in contraindicated in patients with moderate or severe liver impairment (Child-Pugh class B and C)

2. Side effects: Adverse events experienced by > 3% of patients in clinical trials of roflumilast included diarrhea (9.5%), weight loss (7.5%), nausea (4.7%), headache (4.4%) and back pain (3.2%). Patients discontinued therapy due to adverse effects more frequently with roflumilast (14.8%) compared to placebo (9.9%). Diarrhea and nausea were the most common adverse reactions leading to drug discontinuation in prior trials. Serious adverse events that occurred more frequently with roflumilast compared to placebo included diarrhea, atrial fibrillation, lung cancer, prostate cancer, acute pancreatitis acute renal failure. Less common adverse events, (1-2%) of patients that were more frequently reported with roflumilast use as compared to placebo included abdominal pain, anxiety, heartburn, depression, gastritis, rhinitis, sinusitis, muscle spasms, tremor, urinary tract infection, and vomiting. Roflumilast carries a warning for increased psychiatric adverse events and suicidality. Patient should be monitored for changes in mood including worsening insomnia, anxiety or depression or suicidal ideations. Roflumilast also carries a warning for weight loss. 20% of patients may experience moderate weight loss between 5 to 10% of ideal body weight compared to 7% with placebo.

Roflumilast side effects reported in  $\ge 2\%$  of recipients from 8 clinical trials as listed in the manufacturer's package insert are listed in the table below.

Treated with Roflumilast 500 mcg daily and Greater Than Placebo Treatment		
Adverse Reactions	Roflumilast	Placebo
(Preferred Term)	(N=4438)	(N=4192)
	n (%)	n (%)
Diarrhea	420 (9.5)	113 (2.7)
Weight decreased	331 (7.5)	89 (2.1)
Nausea	209 (4.7)	60 (1.4)
Headache	195 (4.4)	87 (2.1)
Back pain	142 (3.2)	92 (2.2)
Influenza	124 (2.8)	112 (2.7)
Insomnia	105 (2.4)	41 (1.0)
Dizziness	92 (2.1)	45 (1.1)

Decreased appetite	91 (2.1)	15 (0.4)

Other side effects reported in 1- 2% of recipients include: Gastrointestinal disorders (abdominal pain, dyspepsia, gastritis, vomiting); Infections and infestations (rhinitis, sinusitis, urinary tract infection); Musculoskeletal and connective tissue disorders (muscle spasms); Nervous system disorders (tremor); and Psychiatric disorders (anxiety, depression).

## 4. O. Drug Interactions with Roflumilast.

## 1. Drugs That Induce Cytochrome P450 (CYP) Enzymes

Strong cytochrome P450 enzyme inducers decrease systemic exposure to roflumilast and may reduce the therapeutic effectiveness of roflumilast. Therefore the use of strong cytochrome P450 inducers (e.g., rifampicin, phenobarbital, carbamazepine, and phenytoin) with roflumilast is not recommended and these medications will be excluded from use in the trial.

#### 2. Drugs That Inhibit Cytochrome P450 (CYP) Enzymes

The co-administration of roflumilast (500 mcg) with CYP3A4 inhibitors or dual inhibitors that inhibit both CYP3A4 and CYP1A2 simultaneously (e.g., erythromycin, ketoconazole, fluvoxamine, enoxacin, cimetidine) may increase roflumilast systemic exposure and may result in increased adverse reactions.

Prior studies have shown that the overall pattern of adverse events in patients with or without roflumilast and long acting beta agonists use is similar. There's no indication from prior studies that roflumilast increases long acting beta agonist related adverse events such as tachycardia or cardiovascular events, and that concomitant long acting beta agonist use does not increase the frequency of events associated with roflumilast treatment alone.

